9.3.2 Recurrent NoV Acute Gastroenteritis (AGE)

Recurrent NoV AGE in a subject is considered a new illness according to the clinical AGE definition (see Section 9.3.1) if the subject has been free from clinical AGE symptoms for at least 5 consecutive days.

If the symptom log for an AGE event contains records of symptoms after the derived end date (i.e., after 5 consecutive days without symptoms, see Section 9.3.1), those symptoms are considered as a potential new AGE event. If any of these records confirms an AGE event as per Section 9.3.1, the date from this record would mark the start of a new AGE event with derived onset and end dates as per Section 9.3.1. If none of these records confirms an AGE event, they will not be reported as new AGE events, but included in the symptoms data listings (as reported).

9.3.3 Acute Gastroenteritis (AGE) Severity

The severity assessment of AGE events will be based on the modified Vesikari scoring (see Appendix A), derived from data collected via the electronic AGE symptoms log, "trigger page" data (both collected in the eDiary), and additional information about the AGE event (treatment and medical attention), collected in the CRF.

If reported start dates for an AGE event differ between the eDiary symptoms log and the Additional Information CRF page, the CRF data with additional information will be attributed to this AGE, if the reported start date on the CRF page is within ±5 days from the start date reported in the eDiary symptoms log.

If more than one Additional Information CRF page is associated with the same AGE event, the page resulting in the worst score (i.e., emergency department visit indicated) will be selected.

The modified Vesikari score (MVS) is composed of seven items:

- 1. Diarrhea duration (days)
- 2. Maximum number loose/liquid stools in 24h (calendar day)
- 3. Vomiting duration (days)
- 4. Maximum number vomiting episodes in 24h (calendar day)
- 5. Maximum recorded body temperature
- 6. Health care provider visits
- 7. Treatment

Each item attributes a subscore ranging from 0 to 3, except for the subscore for treatment, which contributes a maximum of 2 points. The MVS is computed as sum of subscores, with a maximum MVS of 20. For the efficacy analyses and corresponding summaries of the AGE events data, missing subscore will be set to 0. A summary of the AGE events with non-imputed MVS sub-scores will also be provided.

Symptoms (vomiting, loose/liquid stools) and temperature data collected between derived onset and end date for an AGE will be used to determine duration of the symptom, maximum number of episodes and maximum temperature.

Duration of the symptom is defined as the number of calendar days with this symptom present (see Section 9.3.1) between derived onset and end dates.

Number of episodes for a symptom will be calculated for each assessment date (calendar day) as the sum of the number of episodes for 3 8-hour time intervals in the symptoms log. Maximum number of episodes will be derived over days with symptom present. For the records where a trigger page and a symptoms log are completed on the same calendar date, the record with the greatest number of episodes will be used.

Maximum for the temperature will be derived over days when temperature was reported without imputation for the missing records.

The following severity categories will be assigned based on the MVS total score: <9 Mild, 9-10 Moderate, ≥11 Severe.

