15.0 Appendices

Appendix A Vesikari and Modified Vesikari Scoring

	Vesikari Clinical Severity Scoring System ^(a)			Modified Vesikari Score ^(b)			
	Score			Points			
	1	2	3	0	1	2	3
Diarrhea duration, days	1-4	5	≥6	0	1-4	5	≥6
Max. n° of diarrheal stools/24h	1-3	4-5	≥6	0	1-3	4-5	≥6
Vomiting duration, days	1	2	≥3	0	1	2	≥3
Max. n° of vomiting episodes/24h	1	2-4	≥5	0	1	2-4	≥5
Max. recorded body temperature, °C	37.1-38.4	38.5-38.9	≥39.0	≤ 37.0	37.1-38.4	38.5-38.9	≥39.0
Dehydration	N/A	1-5%	≥6%	_	-	-	-
Health care provider visits	-	-	-	None	-	Outpatient ^(c)	ED ^(d)
Treatment	Rehydration	Hospitalization	N/A	None	Rehydration	Hospitalization	-

(a) Adapted from rotavirus clinical trials using the Vesikari clinical scoring system. Mild: <7; Moderate: 7-10; Severe: \geq 11; Maximum score: 20;

^(b) Adapted from Freedman et al. Mild: <9; Moderate: 9-10; Severe: \geq 11 Maximum score: 20;

^(c) Community-based health care provider visit related to vomiting, diarrhea, fever or fluid refusal;

^(d) Emergency room health care provider visit related to vomiting, diarrhea, fever or fluid refusal.

Statistical Analysis Plan (SAP) Version Date: 05-JUN-2024 Sponsor: Hillevax Protocol No: NOR-212

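### SAP 9.3.3 keeps only one care page per AGE, so an ED visit and a hospitalisation recorded on different pages are not both scored

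*SAP*

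**What the plan says.** SAP 9.3.3 builds the MVS from seven items. Five (duration and daily maximum for loose stools and for vomiting, plus maximum temperature) come from the eDiary. The other two come from "additional information about the AGE event (treatment and medical attention), collected in the CRF". On range it says "Each item attributes a subscore ranging from 0 to 3, except for the subscore for treatment, which contributes a maximum of 2 points", and on the total "The MVS is computed as sum of subscores, with a maximum MVS of 20". The severity cut-offs on that total are "<9 Mild, 9-10 Moderate, ≥11 Severe".

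SAP Appendix A gives the points for the two CRF items:

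- health care visit: none 0, outpatient 2, ED 3
- treatment: none 0, rehydration 1, hospitalisation 2

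Protocol Appendix C gives the same points and has no rule for choosing between pages.

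Where more than one Additional Information page is attributed to the same AGE, the SAP says that "the page resulting in the worst score (i.e., emergency department visit indicated) will be selected". No other text combines the two items across pages.

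The eDiary items are treated differently. SAP 9.3.1 resolves several same-day reports symptom by symptom, keeping the largest count for each. SAP 9.3.3 takes episode counts and temperature as maxima over the episode, and durations as counts of days with the symptom.

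The primary endpoint (SAP 11.5.3), the key secondary endpoint (11.5.4) and both other secondary efficacy endpoints (11.5.5) count only moderate or severe AGE, which means MVS 9 or more.

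**The concern.** There are two problems in one sentence.

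1. The main clause selects the page with the worst score, and the parenthesis explains this as the page showing an ED visit. These can be different pages, so two programmers following the same sentence could derive different scores.
2. Visit and treatment are separate items that are added. Keeping one whole page drops whatever scored higher on the other. A child who had both an ED visit and a hospitalisation is credited with both only if they happen to be recorded on the same page.

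The stake is case classification. A lost point or two near the cut-off turns an endpoint case into a mild non-event, or a severe case into a moderate one.

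**Working it through.** **Check of the scale.** Six items with a maximum of 3, and treatment with a maximum of 2: 6 × 3 + 2 = 20. This reproduces the SAP's stated maximum.

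**The two readings conflict.**

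- ED, no treatment: 3 + 0 = 3
- Outpatient, hospitalisation: 2 + 2 = 4

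The parenthesis picks the first page and the main clause picks the second.

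**ED visit and hospitalisation on different pages.** Scoring each item over all pages gives 3 + 2 = 5. The one-page rule gives:

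| Page A | Page B | ED page chosen | Highest-total page chosen | Each item over all pages |
|---|---|---|---|---|
| ED, no treatment (3) | no visit, hospitalisation (2) | 3 | 3 | 5 |
| ED, no treatment (3) | outpatient, hospitalisation (4) | 3 | 4 | 5 |
| ED, rehydration (4) | no visit, hospitalisation (2) | 4 | 4 | 5 |
| ED, rehydration (4) | outpatient, hospitalisation (4) | 4 | 4 | 5 |

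The loss is 1 or 2 points in every row, on either reading.

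**All page pairs.** There are 3 visit levels × 3 treatment levels = 9 possible pages, hence 9 × 8 / 2 = 36 pairs of different pages. Points are lost when one page is higher on visit and the other is higher on treatment: 3 pairs of visit levels × 3 pairs of treatment levels = 9 pairs.

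- ED page chosen (highest total where neither page has an ED visit): 6 pairs lose 1 point and 3 lose 2.
- Highest-total page chosen: 7 pairs lose 1 point and 2 lose 2.

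This count shows where the rule fails. It is not a frequency.

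**Worked case.** Three loose stools and one vomit on one day, temperature 37.0 °C or below. Diarrhoea duration 1, stools 1, vomiting duration 1, vomits 1, temperature 0: subtotal 4. Page 1 is ED with no treatment; page 2 is outpatient with hospitalisation.

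- SAP, ED page: 4 + 3 = 7, mild, not an endpoint
- SAP, highest-total page: 4 + 4 = 8, mild, not an endpoint
- Each item over all pages: 4 + 5 = 9, moderate, meets the severity criterion

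**Which subtotals are affected** (ED and hospitalisation on separate pages; subtotal = symptom and temperature items):

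| Subtotal | Each item over all pages | Rule, 1 point lost | Rule, 2 points lost | Change |
|---|---|---|---|---|
| 3 | 8 | 7 | 6 | none, mild throughout |
| 4 | 9 | 8 | 7 | endpoint lost in both |
| 5 | 10 | 9 | 8 | endpoint lost only with 2 points |
| 6 | 11 | 10 | 9 | severe to moderate in both |
| 7 | 12 | 11 | 10 | severe to moderate only with 2 points |

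From subtotal 8 upwards the total stays at 11 or more under the rule, so the category does not change.

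**The case against.** The strongest reply has two parts.

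First, the operative words are about the worst score, and the parenthesis may be loose wording for an example. Read that way, the conflict between readings disappears and some cases are rescued: with subtotal 5 and the page pair in the worked case, the total is 5 + 4 = 9, still an endpoint. This part stands for such cases. It does not rescue subtotal 4, where the best single page still gives 8, and it does not make the two items count together.

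Second, the Additional Information page carries an AGE start date that is matched to the eDiary within 5 days either way. That would fit one page per reported episode rather than one per visit. If a page covers the whole episode, the ED visit and the hospitalisation sit together and nothing is lost. This stands as a limit on size: the CRF is not among the documents, and they do not explain why several pages arise. It does not remove the defect, because the SAP has a rule for several pages and so foresees them.

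Four stronger readings are tempting, and the documents do not support them:

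- A reader might infer that several pages mean several care contacts, so that the rule specifically under-scores the most medically attended children. The documents do not say this.
- A reader might blame the rule whenever a hospitalised child scores below 9. The scale itself allows that: 3 + 5 = 8 with full scoring.
- A reader might express each lost case as a share of the 24 cases in the sample size section. That is a planning figure, not the observed count, and the number of affected cases is unknown.
- A reader might infer a biased vaccine efficacy estimate. The rule takes no account of trial arm, and the documents give no basis for a direction.

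**Conclusion.** The point holds as a defect in the written derivation. The sentence is internally inconsistent, and on either reading it fails to score an ED visit and a hospitalisation that sit on different pages. The loss is 1 or 2 of 5 points. For that split, endpoint status changes only at subtotal 4, or at 5 when 2 points are lost; severe becomes moderate at subtotal 6, or at 7 when 2 points are lost.

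This rests on the Appendix A points and on more than one page being attributed to the same AGE with the two items split between them. How often that happens cannot be derived from the documents, so no number of lost events, loss of power or bias is claimed. It is worth correcting because it bears on the case definition of the primary, key secondary and other secondary efficacy endpoints and costs almost nothing to remove.

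**What to change.** Before unblinding, replace the page-selection sentence in SAP 9.3.3 with wording such as:

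*Where several Additional Information CRF pages are attributed to one AGE event, the health care provider visit subscore and the treatment subscore are each taken as the maximum over all of those pages.*

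Delete the parenthesis about the emergency department visit. This removes the ambiguity and brings the two CRF items into line with the SAP's use of maxima for episode counts and temperature. It keeps the SAP's own attribution of pages to episodes.

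The cost is one SAP sentence and one line of derivation code. It needs no new data, can be decided on blinded data, and fits the amendment route that SAP 6.0 provides before unblinding. A blinded count of AGEs with more than one page, and of those where the two rules give different MVS categories, would show whether the point matters in practice.

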9.3.4 NoV Presence (Genogroup) and Genotypes

The presence of NoV in the AGE onset stool sample, collected from the subject, and genotype of the NoV will be determined by reverse transcription-polymerase chain reaction(RT-PCR) and RT-PCR sequencing assay; sample testing results (presence of NoV, sequencing and presence of co-pathogens) will be provided via data transfer from a Central Lab. Sequencing assay results will be provided by two different laboratory facilities, hereby referred to as PPD and CDC. The CDC sequencing laboratory results (i.e., results from CDC and PPD), including a summary of agreement between the two laboratory results. Cohen's Kappa will be used to determine the level of agreement. The Kappa statistic, 95% confidence interval and p-value will be presented for subjects in the mFAS. Sequencing results will be reflected in summaries by genotype or endpoint definitions.

The type of stool sample (onset or follow-on), the sample collection date and reported AGE start date are recorded by the site in electronic data capture (EDC) system. If reported start dates for an AGE event differ among the eDiary symptoms log and EDC Stool Sample page, the stool sample data will be attributed to this AGE, if the reported start date on the CRF page is within ±5 days from the start date reported in the eDiary symptoms log.

The derived AGE onset date will be used to determine the window for the corresponding stool sample collection. Samples labelled as 'Onset' by the site and collected between 0 and 6 days after the derived AGE onset date will be included in the efficacy analyses.

If more than one sample is labelled as 'Onset' and available for the same AGE event, the stool sample with the earliest collection date will be used to determine the presence of NoV.

Samples collected later than 6 days from the derived AGE onset date (i.e., collected out of window) may be used in supplementary or exploratory efficacy analysis, if deemed relevant during blind data review.

If the 'Onset' stool sample is collected before the derived AGE onset date but on or after the reported AGE start date, the sample result will be used only if there is at least one episode of any symptom reported in the aforementioned period (between reported AGE start and derived AGE onset).

If the 'Onset' stool sample for an AGE event is missing (not collected), but the first follow on stool sample is collected within the 0 to 6 days window from the derived AGE onset date, this sample will be tested for the presence of NoV, sequencing and presence of co-pathogens, and test results will be used in efficacy analyses.

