8.0 Trial Design

This is a phase 2b, double-blind, randomized, multi-site, placebo-controlled trial to evaluate the efficacy, safety, and immunogenicity of two doses of the intramuscular (IM) HIL-214 vaccine compared to placebo in approximately 3000 children, 5 months of age (-14/+14 days) at the time of the first dose of trial vaccine.

The second dose of trial vaccine should be administered 28 days (and up to 56 days) after the first dose. Trial vaccine doses will be given at least 14 days before or after non-live and orally administered live vaccines, and at least 28 days before or after parenterally administered live vaccines which are given in accordance with country pediatric immunization guidelines. Subjects will be allocated (1:1) into 1 of 2 trial arms by interactive response technology (IRT), stratified by country:

- Arm 1 (N = 1500): One dose of HIL-214 t Visit 1 (Day 1) and one dose of HIL-214 at Visit 2 (28 to 56 days post dose 1)
- Arm 2 (N = 1500): One dose of placebo at Visit 1 (Day 1) and one dose of placebo at Visit 2 (28 to 56 days post dose 1).

A schematic of the Trial Design can be found in Section 6.1 of the protocol.

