8.1 Determination of Sample Size

Collection of 24 primary endpoint cases will provide a power greater than 80% in comparing active vaccine versus placebo in the rate of evaluable first-confirmed AGE cases (moderate or severe) associated with norovirus GI.1 or GII.4 without co-pathogens during the 6 months period if the true vaccine efficacy (VE) is 70%. The underlying assumptions are a 7% annual incidence of moderate to severe AGE attributable to norovirus GI.1 or GII.4, hypothesizing that 40% of norovirus AGE cases are moderate to severe, and 30% are associated with norovirus GI.1 or GII.4 resulting in the 6-month incidence of evaluable primary endpoint AGE cases of 3.5%.

It is expected that enrollment of 3000 subjects will provide sufficient number of cases to demonstrate efficacy, accounting for various rates of drop-out/non-evaluable samples (20% to 30%), and possible lower incidence rate or underreporting of cases.

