11.5 Efficacy Analyses

11.5.1 Hypothesis Testing Strategy and Multiplicity Adjustments

The analysis for the primary efficacy endpoint will be performed at an alpha risk of 5% (two-sided). Statistical analysis of the key secondary efficacy endpoint will be performed only if the primary efficacy endpoint is significant.

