11.5.2 AGE Events

An overview of all AGE events will be provided, including the number of subjects with AGE events, number of AGE events by severity (not available, mild, moderate, severe), number of AGE events per subject by count, number of AGE events by NoV GI genogroup and GII genogroup from first dose until the end of the primary observation period, summarized by trial arm and overall, in the FAS.

For confirmed NoV AGE events with derived onset date from first dose until end of the primary observation period, number of subjects with AGE events, number of AGE events GI positive, and GII positive, number of AGE events by severity (no severity score, mild, moderate, severe, mod/sev), number of AGE events per subjects, number of AGE events by norovirus genotype (genotype, pending, quantity not sufficient, or indeterminate), and without co-infection, with co-infection (each individual pathogen, multiple, any) will be summarized by trial arm and overall, in the FAS and in the PPS-E. This summary will be repeated in the FAS during the primary observation period for medically attended NoV AGEs. It will also be repeated for NoV AGEs from Dose 1 until the end of trial, for NoV AGEs from Dose 1 until Dose 2, and for NoV AGEs from 28 days post dose 2 until the end of the trial in the FAS.

For the first confirmed NoV AGE event with derived onset date in the primary observation period, AGE duration in days, number of days with loose/liquid stools, number of episodes of loose/liquid stools in a day, number of days with vomiting, number of episodes of vomiting in a day, health care provider visits (yes/no), hospitalization for AGE treatment (yes/no), oral rehydration needed (yes/no), subjects treated with IV hydration (yes/no), MVS, severity (not available, mild, moderate, severe) will be summarized descriptively overall and by trial arm using mFAS. This summary will be repeated for primary endpoint AGE events (GI.1 / GII.4 without co-pathogens) and for primary endpoint events in the PPS-E.

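### An onset stool that was collected but gave no usable result can block a usable stool from the same 0-to-6-day window, because SAP 9.3.4 has no valid-result condition

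*SAP*

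**What the plan says.** SAP 9.3.4 admits stools labelled 'Onset' that were collected 0 to 6 days after the derived AGE onset date. It also admits a stool collected before derived onset, on condition that a symptom was reported in the gap. Two further rules matter here.

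- **Several onset stools.** Where more than one is labelled 'Onset' and available for the same event, "the stool sample with the earliest collection date will be used to determine the presence of NoV". The choice is by date. The section does not say what happens if that stool yields no valid result.
- **Follow-on stool as substitute.** The onset stool must be missing, which the SAP explains in brackets as not collected, "but the first follow on stool sample is collected within the 0 to 6 days window from the derived AGE onset date". Only then is the follow-on stool tested for presence, genotype and co-pathogens and used in the efficacy analyses.

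The protocol (6.1) has every onset stool assayed, and sequenced if norovirus-positive. Follow-on stools are by default tested for presence and genogroup only. The schedule in protocol 2.2 has an onset stool up to 6 days after onset and follow-on stools at 7 to 14 and 15 to 21 days.

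The SAP expects some results to be unusable. Among confirmed norovirus events, SAP 11.5.2 tabulates "number of AGE events by norovirus genotype (genotype, pending, quantity not sufficient, or indeterminate". SAP 8.1 includes non-evaluable samples in a 20% to 30% allowance that it shares with drop-out.

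**The concern.** The primary endpoint needs three results from the stool: norovirus present, genotype GI.1 or GII.4, and no co-pathogen. If the deciding stool cannot supply them, the episode cannot count. Under the wording of 9.3.4 this can happen in two ways although a usable in-window stool exists:

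1. Two onset stools were taken and the earlier one failed. The later one is not used for presence.
2. One onset stool was collected and failed, and a follow-on stool was taken by day 6. The onset stool is not missing in the SAP's sense, so the follow-on route stays shut. The default follow-on testing gives no genotype.

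In both situations a moderate or severe episode that may be a true endpoint case is handled as a non-case. This touches the primary endpoint and all the secondary efficacy endpoints. Power depends on a modest case count, and SAP 9.2.6 records that the 6-month period has been chosen, so the 8-month extension is no longer there to make up lost cases.

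**Working it through.** **1. The plan's own figure.** Inputs: 24 cases and true VE 70%, so hazard ratio 0.30 (SAP 8.1); two-sided 5% (SAP 11.5.1); 1:1 allocation (SAP 8.0). Schoenfeld's formula:

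- power = Φ(√(D × 0.25) × |ln HR| − 1.96)
- D = 24: √6 × 1.204 = 2.949; Φ(2.949 − 1.96) = Φ(0.989) = 83.9%

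This reproduces the SAP's claim of more than 80%. A Wald interval conditional on 24 events gives 83.1%. Freedman's formula (75.1%) and the exact conditional binomial (69.1%) are lower, but Schoenfeld matches the planned Cox model and is used below.

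**2. Loss that would matter.** Cases needed for 80% power: (1.96 + 0.842)² / (0.25 × 1.204²) = 21.66. Starting from 24, the tolerable loss is 1 − 21.66/24 = 9.75%.

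**3. Loss the rule could cause.** A case is lost only if a second in-window stool exists *and* the first stool is unusable *and* the second is usable. The documents give none of these rates. Assume that 2% to 5% of events have a second in-window stool, that 5% to 30% of first stools fail, and, generously to the concern, that the second stool always works.

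| | Second stool | First fails | Share lost | Of 24 cases |
|---|---|---|---|---|
| Low | 2% | 5% | 0.1% | 0.024 |
| High | 5% | 30% | 1.5% | 0.36 |

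The 30% is a high-end assumption, since the allowance in SAP 8.1 pools drop-out with non-evaluable samples.

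**4. Effect on power.** At the high end D = 24 − 0.36 = 23.64: √5.91 × 1.204 = 2.927; Φ(0.967) = 83.3%, against 83.9% without loss. Larger losses are beyond the assumed range: 5% lost gives 82.0%, and 10% lost gives 79.9%. With 30% first-stool failure, reaching the 9.75% limit would need 0.0975/0.30 = 32.5% of events to have a second in-window stool.

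At the planned accrual there is more room. Expected cases are 1500 × 3.5% = 52.5 on placebo and 52.5 × 0.30 = 15.75 on vaccine, 68.25 in all; after the 20% to 30% allowance, 54.6 to 47.8. Power then stays at or above 96% even with a further 20% loss.

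**5. Effect on VE.** An equal loss share in both arms cancels in the ratio, and VE stays at 70%. In the extreme where the whole 1.5% falls in one arm:

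- vaccine only: 1 − 0.30 × 0.985 = 70.5%
- placebo only: 1 − 0.30/0.985 = 69.5%

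**The case against.** The strongest reply is that the situation is off-protocol and rare. One onset stool is requested per episode, and a follow-on stool before day 7 is ahead of schedule. Sequencing results come from two laboratories, which may rescue some genotypes from the same stool. Non-evaluable samples are already allowed for. A date-only rule is also objective and cannot be steered by results. All of this stands as an argument that the effect is small. It does not supply the missing fallback, and the SAP itself thought an in-window follow-on stool worth a rule.

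The reading of the first rule can be contested too. The word 'available' might mean with a result available, but the SAP does not define it. The earliest-date sentence speaks of norovirus presence, and the failures listed in SAP 11.5.2 are genotype failures among confirmed events, so they do not show that presence tests fail. Blocking a later stool for genotype is therefore an inference from the absence of a fallback. The bracketed condition on the follow-on stool is not ambiguous in this way.

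Three stronger readings are tempting and are not supported:

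- **That the rule costs about one case in 24.** This counts every event with a second stool as lost. The first stool must also be unusable.
- **That it could overturn the primary result.** With a Wald lower bound of 1 − (a/b) × exp(1.96 × √(1/a + 1/b)), vaccine:placebo splits of 7:18, 7:17 and 7:16 give 6.9%, 0.7% and −6.3%. But 7:18 is a chosen borderline (VE 61%), and only placebo cases are removed. Losing a vaccine case instead (6:18) raises the bound to 16.0%. At the planned 24 cases and VE 70%, the split is about 5.5:18.5; from 6:18, losing two placebo cases (6:16) still leaves 4.2%.
- **That the earliest-date rule could select a pre-onset stool that the section bars.** Read as a whole, the section excludes an ineligible stool before the earliest is chosen.

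**Conclusion.** The gap is real and small. SAP 9.3.4 does not require a valid result when it picks among onset stools, and it opens the follow-on route only when the onset stool was not collected. No other section offers a fallback, so following the text exactly can set aside a usable in-window stool. The child is not removed or permanently classed as event-free: follow-up continues, and a later qualifying episode in the period still counts.

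On the assumed 2% to 5% and 5% to 30%, the loss is about 0.02 to 0.4 of 24 cases, or at most about half a percentage point of power. VE is unbiased if the loss is equal across arms. The true frequency is not in the documents, so the size rests on those assumptions. The reason to act is that this is a primary endpoint derivation which can be coded in two ways and is cheap to settle. The sample size does not need to change.

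**What to change.** Amend SAP 9.3.4 and apply the change blinded to arm, before unblinding:

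1. **Onset stools.** Use the earliest eligible onset stool (days 0 to 6, or the pre-onset exception where its symptom condition is met) that has valid results for the tests the endpoint needs. A valid negative result stands, so the fallback cannot be used to search for positives.
2. **Follow-on stool.** Change the trigger to: *missing, or collected without a valid result*. Keep the 0-to-6-day limit.
3. **Source of results.** Take presence, genotype and co-pathogens from the same stool where possible. An endpoint associated only with given genotypes is harder to interpret if the results come from different days, so flag in a listing any event that combines stools.

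The cost is a paragraph of SAP text and full testing of a few stored in-window follow-on stools, a kind of testing that 9.3.4 already provides for. Second onset stools should need little or no extra work, since the protocol already has all onset stools assayed, and sequenced and tested for co-pathogens if norovirus-positive.
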